7.1.1.4 Analysis Methods

Primary endpoint analyses for regulatory approval will be done on consecutive subjects, and according to the requirements of the guidance documents:

- ISO5840:2009: for regulatory submissions in geographies adhering to the ISO5840:2009 standards (minimum of 150 subjects with 1 year follow up and 400 patient years)
- FDA Heart Valve Guidance 2010 for US FDA PMA (minimum of 300 subjects with 1 year follow up and 800 patient years).

Early rates of adverse events will be calculated as the number of early adverse events divided by the total number of subjects, expressed as a percentage. Early events are events occurring on or before 30 days post-operative.

Linearized rates will be calculated as the number of late events divided by the cumulative late post-operative patient-years, expressed as a percentage. Late events are events occurring after 30 days post-operative. For those adverse events with OPC available, the linearized rates and their associated one-sided upper 95% confidence bounds will be compared to 2 x the OPC rate to show that they are within acceptable limits.

Kaplan-Meier survival analyses will also be performed to summarize the adverse event data.

In addition, control articles based on current literature of previously approved heart valves will be selected. Adverse event data from the control articles will be provided so as to inform the reader of the current state of heart valve technology, as expressed by articles in quality peer-reviewed journals, and allow additional evaluation of the Model 400 adverse event data.

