6.2 Rationale for Choice of Hypothesis

As the OPC presented in Table 1, Valve Thrombosis, Major Hemorrhage and Major PVL rate are all less than 1.2% per patient-year, and to achieve the 80% power for these tests, a much larger sample size is required to evaluate these rare events. For example, to detect a Major Paravalvular Leak rate of 0.6% per patient-year, more than 1800 patient-years of data are required; and to detect a Valve Thrombosis rate of 0.2% per patient-year, more than 5000 patient-years of data are required. Such a large sample size requirement may leave the trial un-executable. Thus, the smallest acceptable adverse event rate of 1.2% per patient-year (excluding Valve Thrombosis, Major Hemorrhage and Major PVL) is chosen for the sample size assumption.

7. Statistical Methods

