7.2 General Methodology

7.2.1 Reports for which this Statistical Analysis Plan Applies

This SAP applies to the trial report for Pre-market Approval Application (PMA) to the Food and Drug Administration (FDA) and the final report.

This SAP applies to the trial report for CE mark submission and to the report for regulatory submissions in other geographies.

The analyses for CE mark approval and FDA approval may be used for regulatory submissions in other geographies.

This SAP applies to the main trial manuscript, though the manuscript may not include all analyses specified in this document.

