7.2.2 Special Considerations

7.2.2.1 Report Timing and Cutoff Dates

Cutoff dates will be applied to all site case report forms. A Visit Cutoff Date and a Received Cutoff Date will be used. The visit cutoff date will be the first date on which at least 800 patient-years of data have been collected for the PMA report. The visit, assessment, and event dates will be used to determine which case report forms satisfy the visit cutoff date. The received cutoff date will be determined near the time of the database closure and will be chosen to ensure that all forms of critical importance have been received while still allowing adequate time for data cleaning between the received cutoff date and the date of database closure. The "logints" log-in timestamp field will be used to determine which case report forms satisfy the received cutoff date. CE mark report Visit Cutoff Date and a Received Cutoff Date will be used similarly when regulatory submission data requirement is met.

Any forms which do not have a visit date directly on the form will use the visit date from the corresponding form for that entry. Forms with multiple dates will apply cutoff dates to individual lines of data on the form.

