7.2.2.3 P-Values

The statistical test for the safety objective will be performed at one-sided α =0.05. All reported p-values greater than or equal to 0.0001 will be rounded to four decimal places. P-values less than 0.0001 will be displayed as "<0.0001."

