7.9.1.3 Data Collection and Analysis Methods

7.9.1.3.1 Data Collection and Analysis

Adverse device effects and outcomes will be identified and reported by the Investigator at all visits. All deaths and endpoint related adverse events will be reviewed by the CEC.

Early postoperative events are defined as those occurring on or before 30 days post-operative. Late postoperative events are those occurring after 30 days post-operative.

Early rates of adverse events will be calculated as the number of early adverse events divided by the total number of subjects, expressed as a percentage.

The late events rates will be calculated using the linearized event rate methodology. That is, the rate will be the number of late events divided by the late post-operative patient-years. For those adverse events with OPC available, the linearized rates and their associated one-sided upper 95% confidence bounds will be compared to the Objective Performance Criteria (OPC) to show that they are within acceptable limits. Formally, the method introduced by Cox^{iv} which gives the relatively most accurate results^v will be used:

χ .95,2 n_e +1/2Y_T

where ne is the number of late events and YT is the late post-operative patient-years. If there is 0 events, the one-sided upper 95% confidence bound will be 0.

Kaplan-Meier survival analyses will also be performed to summarize valve-related adverse events and death. The Kaplan-Meier rate and the corresponding 95% confidence interval will be presented for each visit interval. In addition, number of subjects at risk, number of events, number of censored subjects and the Kaplan-Meier survival curve or event curve will also be displayed.

In addition, control articles based on current literature of previously approved heart valves will be selected. Adverse event data from the control articles will be provided so as to inform the reader of the current state of heart valve technology, as expressed by articles in quality peer-reviewed journals, and allow additional evaluation of the Model 400 adverse event data.

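### Setting the upper confidence bound to 0 when no late events occur gives valve thrombosis a type I error of about 20% at 400 late patient-years, and prints a false bound for any OPC event with no late events

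*SAP*

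**What the plan says.** Protocol 7.1.1.2 and SAP 7.9.1.2 set the null hypothesis for each OPC event: the true late linearized rate is at least twice the OPC. Protocol Table 8 lists seven such events. Valve thrombosis has the lowest OPC, 0.2% per patient-year, so its limit is 0.4%. SAP 7.2.2.3 fixes the level: "The statistical test for the safety objective will be performed at one-sided α =0.05".

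The decision is made by comparing an upper bound with a limit. In protocol 7.1.1.4 the "one-sided upper 95% confidence bounds will be compared to 2 x the OPC rate to show that they are within acceptable limits". In SAP 7.9.1.3.1 the "one-sided upper 95% confidence bounds will be compared to the Objective Performance Criteria (OPC) to show that they are within acceptable limits", without the factor of two. The SAP obtains the bound from the Cox approximation. The formula is broken in the text available; I read it as chi-square(0.95, 2n+1)/(2Y), with n late events and Y late patient-years. It then overrides that formula: "If there is 0 events, the one-sided upper 95% confidence bound will be 0". The protocol has no zero-event rule.

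Protocol 7.1.1.4 sets the exposure for ISO 5840 submissions at a "minimum of 150 subjects with 1 year follow up and 400 patient years", and for the FDA at 800 patient-years. SAP 7.2.1 covers both routes: "This SAP applies to the trial report for CE mark submission and to the report for regulatory submissions in other geographies", as well as the PMA and final reports. SAP 6.2 leaves valve thrombosis out of the sample-size basis because "to detect a Valve Thrombosis rate of 0.2% per patient-year, more than 5000 patient-years of data are required". It does not remove thrombosis from the events that are tested.

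**The concern.** An upper confidence bound gives the largest rate still compatible with the data. No finite follow-up without events excludes every positive rate, so the bound cannot be 0. Once it is set to 0, any OPC event with no late events meets its criterion however short the follow-up.

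This matters most for the rarest event. Valve thrombosis has a limit of 0.4% per patient-year, and zero events is a plausible result in a few hundred patient-years even at that rate. The rule would then certify as acceptable a rate that the data cannot rule out. Where the verdict does not change, a table showing an upper 95% bound of 0% still misstates what was learned.

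**Working it through.** **The plan's own figure.** SAP 6.1 asks for about 800 patient-years to test 2.4% against a true 1.2% (one-sided alpha 0.05, power at least 80%, Poisson). An exact search gives a smallest exposure of 811 patient-years, with critical count 12, alpha 0.0495 and power 0.816. That agrees with the stated figure to within 3%.

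**Formulas at zero events.**
- Exact one-sided 95% Poisson bound: chi-square(0.95, 2)/(2Y) = -ln(0.05)/Y = 2.996/Y.
- Cox bound as read above: chi-square(0.95, 1)/(2Y) = 3.841/(2Y) = 1.921/Y.
- Probability of zero events at the limit: exp(-0.004 x Y) for thrombosis.

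**Valve thrombosis, limit 2 x 0.2% = 0.4% per patient-year, zero late events.**

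| Late patient-years | SAP bound | Cox bound | Exact bound | P(0 events) at a true 0.4% |
|---|---|---|---|---|
| 400 | 0 | 0.480% | 0.749% | exp(-1.6) = 0.2019 |
| 480 | 0 | 0.400% | 0.624% | 0.1465 |
| 749 | 0 | 0.256% | 0.400% | 0.0500 |
| 800 | 0 | 0.240% | 0.374% | exp(-3.2) = 0.0408 |

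At 400, one event gives a Cox bound of 7.815/800 = 0.977% and an exact bound of 9.488/800 = 1.186%. Both exceed 0.4%. Zero is therefore the only count that passes, and the type I error under the SAP rule is the whole of P(0) = 20.2%. Without the rule, both formulas put the zero-event bound above 0.4%, so thrombosis cannot pass at 400.

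**The other six OPC events.** Late patient-years at which zero events meets 2 x OPC under the exact bound (2.996 divided by the limit):

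| Event | 2 x OPC | Late patient-years needed |
|---|---|---|
| Thromboembolism | 5.0% | 59.9 |
| All hemorrhage | 2.8% | 107.0 |
| All paravalvular leak | 2.4% | 124.8 |
| Endocarditis | 2.4% | 124.8 |
| Major hemorrhage | 1.8% | 166.4 |
| Major paravalvular leak | 1.2% | 249.6 |
| Valve thrombosis | 0.4% | 748.9 |

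At 400 or more, only thrombosis has its verdict changed. For the other six, the printed 0 is wrong but the pass is legitimate.

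**Late or total patient-years.** The bound divides by late years, but the plan does not say that its 400 and 800 minimums are late years. Assume they are totals and every implanted subject passes day 30, so that late = total - N x 30/365.25.
- Total 400, N from 150 to 650 (assumed range): 388 to 347 late years, type I error 21% to 25%.
- Total 800, N = 650: 746.6 late years, exact bound 0.401%, type I error 5.05%.
- Total 800, N = 1300: 693.2 late years, exact bound 0.432%, type I error 6.25%.

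**If the SAP's 1 x OPC comparator were applied literally.** A zero-event pass would need 2.996/0.002 = 1498 late patient-years for thrombosis and 2.996/0.006 = 499 for major paravalvular leak. The other five need at most 333. The zero rule would then change the thrombosis verdict at 800, and the thrombosis and major paravalvular leak verdicts at 400.

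**The case against.** The strongest reply is that the effect is narrow.

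- **Exposure.** The 400 patient-years are a minimum, not a planned cutoff. For the PMA, "The visit cutoff date will be the first date on which at least 800 patient-years of data have been collected for the PMA report", and at 800 late years the thrombosis verdict is correct. The staged analysis at 200 and 400 patient-years uses a composite Z test that this rule does not touch.
- **Timing.** This SAP revision follows CIP 1F, dated March 2019, and the 19 to 27 mm sizes were approved in 2017. Later reports should lie well above 749 late patient-years, where only the printed bound is wrong. Event counts and Kaplan-Meier results appear beside it.
- **Rows affected.** The SAP defines the bound only for events with an OPC.
- **Critical-count rule.** SAP 6.1 also states rejection through a critical count with tail probability at most alpha. At 400 patient-years no such count exists for thrombosis, so that rule would not reject.
- **N = 1300.** SAP 6.1 expects up to 650 implants to yield 800 patient-years, so this case fits the plan poorly.
- **A simpler fix.** Deleting the sentence and keeping the Cox formula gives the right verdict at both 400 and 800 late patient-years.

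The limits on scope stand. They do not defend the sentence. Protocol 7.1 and 7.1.1.4 send the per-event analysis to CE mark at the ISO minimum, so the 400 case is within the plan. The critical-count rule sits in the sample-size section and contradicts the zero-event sentence; it does not override it, because both documents make the decision by comparing bounds. The Cox-only repair still passes thrombosis from 480 to 749 late patient-years, with type I error falling from 14.65% to 5%.

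**Conclusion.** The concern holds. A stated decision rule gives a wrong result and should be fixed.

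For valve thrombosis at 400 late patient-years, the type I error is 20.2% against a stated 5%. The inflation shrinks as exposure grows and ends at about 749 late patient-years. No other OPC event has its verdict changed against 2 x OPC at 400 or more. At 800 late patient-years the decision is right. If 800 is total exposure, the excess is small: 5.05% at 650 implants.

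For reports with long follow-up, the main harm is a false 0% bound beside each OPC event with no late events. These figures assume Poisson counts at a constant late rate, the 2 x OPC limit, and 400 read as late years; reading it as total exposure makes the error somewhat larger.

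**What to change.** 1. In SAP 7.9.1.3.1, delete the zero-event sentence. State that with no late events the bound is the exact Poisson value, chi-square(0.95, 2n+2)/(2Y), which is 3.00/Y at n = 0, and that zero events pass only if this is below 2 x OPC.
2. In the same paragraph, change the comparator to 2 x OPC.
3. State whether the 400 and 800 patient-year minimums are late patient-years.

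Items 1 and 2 are two SAP sentences and one line of code. Item 3 is a clarification that also bears on protocol 2.2 and 7.1.1.4 and SAP 5 and 7.2.2.1.

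The consequence is that zero-event bounds become less favourable, and valve thrombosis cannot be shown to meet its criterion below about 749 late patient-years. The report should say so.

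Using the exact bound only at n = 0 mixes two methods. Using it throughout is cleaner but stricter: at 800 patient-years and an OPC of 1.2%, the largest passing count falls from 12 (alpha 0.0556, power 0.828) to 11 (alpha 0.0315, power 0.741). The sponsor should choose one and write it down.

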7.9.1.3.2 Determination of Data for Analysis

All subjects who are enrolled in the trial and have a trial valve implanted will be included for analysis.

For subjects who are attempted but not implanted, their data will be summarized separately.

7.9.2 Effectiveness Objective

The effectiveness objective is to confirm the effectiveness of the Model 400 valve, with regard to NYHA Functional Classification and hemodynamic performance.

Revision 7.0

Page 19 of 22

7.9.2.1 Endpoints

The effectiveness endpoints are

NYHA Functional Classification (at discharge (or 30 days), 3-6 months, 1 year • and annually thereafter through 5 years) is a classification system for defining cardiac disease and related functional limitations into four broad categorizations:

Class I	Subject with cardiac disease but without resulting limitations of physical activity. Ordinary physical activity does not cause undue fatigue, palpitation, dyspnea, or anginal pain.
Class II	Subjects with cardiac disease resulting in slight limitation of physical activity. They are comfortable at rest. Ordinary physical activity results in fatigue, palpitation, dyspnea, or anginal pain.
Class III	Subjects with cardiac disease resulting in marked limitation of physical activity. They are comfortable at rest. Less than ordinary physical activity causes fatigue, palpitation, dyspnea, or anginal pain.
Class IV	Subjects with cardiac disease resulting in inability to carry on any physical activity without discomfort. Symptoms of cardiac insufficiency or of the anginal syndrome may be present even at rest. If any physical activity is undertaken, discomfort is increased.

- Hemodynamic Performance (at discharge (or 30 days), 3-6 months, 1 year and annually thereafter through 5 years) including
 - effective orifice area (EOA)
 - effective orifice area index (EOAI) 0
 - peak pressure gradient 0
 - mean pressure gradient 0
 - valvular regurgitation 0
 - performance index 0
 - cardiac output 0
 - 0 cardiac index

7.9.2.2 Hypothesis

No formal hypothesis will be evaluated for this objective. Control articles based on current literature of previously approved heart valves will be selected. Data from the control articles will be provided so as to inform the reader of the current state of heart valve technology, as expressed by articles in guality peer-reviewed journals, and allow evaluation of the Model 400 data.

7.9.2.3 Data Collection and Analysis Methods

NYHA functional classification and hemodynamic data will be summarized using descriptive statistics for continuous variables and frequency tables for discrete variables.

NYHA functional class will be evaluated based on the percentage of subjects in each specific NYHA class at each postoperative time-point and the percentage of subjects at each postoperative time-point who have improved, worsened, or not changed in NYHA class compared to preoperative baseline.

Medtronic PERIGON Pivotal Trial Statistical Analysis Form Plan Revision 7.0 Page 20 of 22 Medtronic

All echocardiograms will be analyzed by an echo core lab which will determine the values for the Hemodynamic Performance endpoints. Valvular regurgitation will be summarized with a frequency table for each visit interval and the other Hemodynamic Performance endpoints will be summarized as with continuous data. For each subject with paired data, the change from baseline may also be calculated at discharge (or 30 days), 3-6 months, 1 year and annually thereafter through 5 years. These data will be summarized by valve size.

Control articles based on current literature of previously approved heart valves will be selected. Effectiveness data from the control articles will be provided so as to inform the reader of the current state of heart valve technology, as expressed by articles in quality peer-reviewed journals, to allow for evaluation of the Model 400 valve effectiveness data.

7.9.3 Additional Analyses

Additional analyses will be performed on the implanted population for safety and effectiveness data.

7.9.3.1 Safety Endpoints

The safety endpoints include the valve-related adverse events of Thromboembolism, PVL, reoperation, explant and all-cause mortality. Events that occurred in less than five subjects will not be evaluated by the additional analyses.

The additional safety endpoint analyses described in Section 7.9.3.1 will be included in regulatory submissions to all geographies except for Risk Factor Analysis which will be included only in the submission in US.

7.9.3.1.1 Valve Size Analysis

The evaluation of the effect of valve size over time to the valve-related adverse events and death will be performed as follows:

Cox Proportional Hazards model will be used to evaluate the valve size effect on valve-related adverse events and death.

Due to possible small sample sizes in the smallest and largest valve sizes, the 17 mm may be combined with the 19 mm and the 27 mm may be combined with the 29 mm size to create larger groups of valve sizes. Thus, four indicator variables for valve size (representing 17 mm to 19 mm, 21 mm, 23 mm, 25 mm, and 27mm to 29 mm) may be created and included in the model.

Valve size will be considered to be significantly associated with time to valve-related adverse events and death if the p-value <0.05.

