7.9.3.1.2 Gender Analysis

Assessment of the possible gender differences will be examined in the freedom from (or event rate) valve-related adverse events and death after implantation of the Model 400 valve.

The possible gender differences in the event rates of death and valve-related adverse events will be evaluated using the log-rank test.

Differences in gender will be considered to be significant if the p-value<0.05.

Revision 7.0

Page 21 of 22

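### The valve-size Cox model is unadjusted, so if size is linked to gender and gender affects risk, a gender difference can be reported as a size association.

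*SAP*

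**What the plan says.** SAP 7.9.3.1 names the endpoints for the additional safety analyses: "The safety endpoints include the valve-related adverse events of Thromboembolism, PVL, reoperation, explant and all-cause mortality". It sets a floor: "Events that occurred in less than five subjects will not be evaluated by the additional analyses".

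For valve size, SAP 7.9.3.1.1 states that a "Cox Proportional Hazards model will be used to evaluate the valve size effect on valve-related adverse events and death". Because the extreme sizes may be sparse, "the 17 mm may be combined with the 19 mm and the 27 mm may be combined with the 29 mm size". This leaves five groups, and the four resulting indicators "may be created and included in the model". No other covariate is named. The decision rule is: "Valve size will be considered to be significantly associated with time to valve-related adverse events and death if the p-value <0.05".

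Gender is handled separately in SAP 7.9.3.1.2: "The possible gender differences in the event rates of death and valve-related adverse events will be evaluated using the log-rank test". No adjustment for size is mentioned.

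SAP 7.9.3.1.3 puts gender and valve size in one Cox model, with age at implant, NYHA class, previous aortic valve replacement and concomitant CABG. It covers all-cause death, reoperation and explant, and uses backward elimination until every remaining factor has p below 0.15. On reporting, SAP 7.9.3.1 sends the additional safety analyses to all geographies "except for Risk Factor Analysis which will be included only in the submission in US".

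**The concern.** Valve size is not assigned by design. The trial is non-randomized, and Protocol section 9 describes sizers used to pick the size that suits the patient. Size is therefore partly a patient characteristic. SAP 7.3 lists gender and age at implant among its possible clinically meaningful baseline risk factors, and Protocol 7.3.5 gives assessing characteristics that may influence endpoints as a reason for collecting demographics. The size model uses none of this.

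With size tested without gender and gender tested without size, one underlying difference could surface twice, once under each name. A reader of the size result would want to know whether some sizes behave differently. An unadjusted test also responds to who receives each size, and the plan gives no way to separate the two for thromboembolism, for paravalvular leak, or for any endpoint in a non-US report.

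**Working it through.** **1. Where an adjusted size estimate is planned**

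| Analysis | Size and gender together? | Endpoints | Where reported |
|---|---|---|---|
| SAP 7.9.3.1.1, valve size | No, size only | All five, if the event floor is met | All submissions |
| SAP 7.9.3.1.2, gender | No, gender only | Death and valve-related events | All submissions |
| SAP 7.9.3.1.3, risk factors | Yes, but gender is removable at p ≥ 0.15 | Death, reoperation, explant | US only |
| SAP 7.3, center pooling | Only if the site p-value is ≤ 0.15; the target is the site effect | Valve-related events | Not a size analysis |

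Two of the five endpoints have no joint risk-factor model anywhere, and none of the five has one outside the US.

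**2. Inputs for sizing the effect**

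The plan gives no event count, power or hazard ratio for this analysis, so there is no figure to reproduce. From the SAP: five size groups, a 4-df test, alpha 0.05 (critical value 9.488). Assumed: no true size effect; equal follow-up; size mix p = 6/22/34/27/11% for 17–19, 21, 23, 25 and 27–29 mm; gender hazard ratio 1.5 or 2; 30, 60 or 120 events. The proportion of women w in each size group is

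- strong link: 85/55/20/5/2% (0.051 + 0.121 + 0.068 + 0.0135 + 0.0022 = 25.6% women overall);
- milder link: 55/40/25/15/8% (0.033 + 0.088 + 0.085 + 0.0405 + 0.0088 = 25.5% women overall).

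**3. Apparent size effect from gender alone**

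Relative to men, the average hazard in group k is h_k = 1 + (HR − 1)·w_k. Smallest against largest group:

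- strong, HR 2: 1.85/1.02 = 1.81; HR 1.5: 1.425/1.01 = 1.41;
- milder, HR 2: 1.55/1.08 = 1.44; HR 1.5: 1.275/1.04 = 1.23.

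**4. Rejection rate of the unadjusted test**

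With D events, the size statistic is approximately noncentral chi-square on 4 df with λ = D·Σ p_k(h_k/h̄ − 1)², where h̄ = Σ p_k h_k.

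Worked case (strong link, HR 2): h̄ = 1.2557 and h_k/h̄ = 1.473, 1.234, 0.956, 0.836, 0.812. The sum is 0.0134 + 0.0121 + 0.0007 + 0.0072 + 0.0039 = 0.0373. At 60 events λ = 2.24, and the chance of exceeding 9.488 is 0.188.

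| Link | Gender HR | 30 events | 60 events | 120 events |
|---|---|---|---|---|
| Milder | 1.5 | 0.055 | 0.060 | 0.070 |
| Milder | 2 | 0.066 | 0.083 | 0.120 |
| Strong | 1.5 | 0.068 | 0.087 | 0.130 |
| Strong | 2 | 0.113 | 0.188 | 0.357 |

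**5. Simulation, without and with gender in the model**

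Grouped Poisson likelihood-ratio test as a stand-in for Cox, 1500 runs per cell, same assumptions (unadjusted / gender-adjusted):

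| Link | Gender HR | 30 events | 60 events | 120 events |
|---|---|---|---|---|
| Milder | 1.5 | 0.064 / 0.058 | 0.067 / 0.059 | 0.073 / 0.059 |
| Milder | 2 | 0.083 / 0.062 | 0.084 / 0.052 | 0.124 / 0.055 |
| Strong | 1.5 | 0.085 / 0.060 | 0.106 / 0.056 | 0.138 / 0.047 |
| Strong | 2 | 0.136 / 0.057 | 0.203 / 0.063 | 0.351 / 0.049 |

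Other seeds and other assumed size mixes moved single cells by a few percentage points. Across these settings the unadjusted rate is about 6–12% (milder link) and about 6–36% (strong link). The adjusted rate is about 5–8%.

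**6. Check of the null cases**

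With gender HR 1, or with the same size distribution in both sexes, simulated rates were about 0.04 to 0.07 for both models. The inflation needs both conditions.

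**The case against.** The strongest reply is that the premise is not in the documents. Neither document links valve size to gender or body size, gives a size distribution by gender, or says that women carry higher risk. This stands. A reader might infer that the trial will report a gender difference as a size effect; the documents support only that it could. With a milder link and a gender hazard ratio of 1.5 the inflation is small.

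Second, the rule speaks only of association. If some sizes go to higher-risk patients, size is associated with events, and a rejection is not an error for the rule as worded. This also stands, but readers will be tempted to take the result as a property of the valve, and the unadjusted model cannot support that.

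Third, a reader might infer that this is the only planned safety comparison across sizes. It is not: SAP 7.9.3.1.3 includes size with gender for three endpoints, SAP 7.3 may hold both variables, and SAP section 3 allows further analyses. These narrow the gap without closing it, for the reasons in the comparison of models.

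Fourth, a reader might infer that the two investigational sizes, 17 mm and 29 mm, are overlooked. Merging them is optional and is justified by small numbers. SAP 7.2.2.5 plans for each size separately, and SAP 7.10 lists all adverse events and deaths. With as few as the 15 valves per size anticipated in Protocol 2.1, a stand-alone hazard ratio could say little.

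Finally, more covariates strain sparse endpoints. Four indicators plus gender plus age make six coefficients, against a floor of five subjects with events. That limits the fix.

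**Conclusion.** The point holds in a limited form. The size model is unadjusted in a non-randomized trial where size is fitted to the patient, and no planned analysis gives an adjusted size estimate for thromboembolism or paravalvular leak, or for any endpoint outside the US. For the three endpoints that do have a joint model, gender can be eliminated while size stays.

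The size of the problem rests on assumed inputs: about 6–12% false size signals under a milder link and about 6–36% under a strong one, for gender hazard ratios of 1.5 to 2 and 30 to 120 events. If either condition is absent there is no inflation.

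This is an additional analysis. The OPC comparisons, the sample size and the interim test do not depend on it, and nothing here should be read as questioning them. The change is still worth making, because it uses baseline data already collected and variables the SAP already treats as risk factors.

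**What to change.** In SAP 7.9.3.1.1:

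- Force gender into the valve-size Cox model for each evaluated endpoint, and age at implant where event counts allow.
- Report the unadjusted result alongside, include both in all submissions, and base any statement of a size effect on the adjusted estimate.
- For endpoints with few events, adjust for gender only or report descriptively, and say in advance which rule applies.

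Keep the size indicators. Size in mm as a single linear term is at most a supplementary trend summary. In simulations at 120 events with the strong-link mix, both models gender-adjusted, the linear term had about 74% power against 53% for the indicators when the truth was log-linear (HR 0.88 per mm). When risk was doubled at both ends of the size range, it had 9% against 75%.

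Optionally, show events and late patient-years for 17 mm and 29 mm as separate descriptive rows, whatever grouping is modelled.

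The cost is a few sentences in the SAP, a few lines of code, and a somewhat wider interval for the size effect. Gender and age may capture body size only in part, so some confounding could remain and the report should say so.
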